#### 8.4.4 Covariates

Patient characteristics at baseline will be assessed for Tio+Olo and LABA/ICS users overall and stratified by history of exacerbation, circulating eosinophils, subgroups defined by both exacerbation and eosinophil levels.

We will identify and describe the following demographic characteristics as of the index date:

- Sex
- Age (years, as both a categorical and a continuous variable)
- Calendar year of cohort entry
- Season of index date (winter, spring, summer, fall)
- US census region of residence
- Insurance type (e.g., Commercial, Medicare)

Additional characteristics will be defined during the 12-month pre-index baseline period:

- Number of previous COPD treatments
- Specific previous COPD treatments
  - o LAMA monotherapy
  - o LABA monotherapy
  - o ICS monotherapy
  - o LAMA/ICS combination therapy
- Previous acute COPD exacerbation (measured both overall and in the 30 days prior to cohort entry), categorized as 0, 1, or 2+.
  - All exacerbations (Moderate+Severe)
  - o ED visits or dispensings of inhaled corticosteroids/antibiotics (Moderate)
  - o Hospitalizations (Severe)
- Use of other respiratory drugs in the 12-month pre-index period::

- Short-acting beta-agonists
- Anticholinergics

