#### Exclusion Criteria:

- 1. To increase the likelihood of a true diagnosis of COPD, we will exclude:
  - a) All patients less than 40 years of age on the index date, and
  - b) All patients with a diagnosis of asthma in the year prior to the index date
- 2. To limit the population to those without severe lung compromise outside of COPD, we will exclude individuals with lung cancer, interstitial lung disease, or lung transplant identified at any time prior to the index date
- 3. To restrict the cohort to new users of Tio+Olo or LABA/ICS, we will exclude any individual with use of either Tio+Olo, LABA/ICS, or LABA/LAMA/ICS

combination therapy in free or fixed form for at least one year prior to the index date.

Outpatient laboratory data is available for a subset of patients. Some analyses will be further restricted to the subset of the population with at least one laboratory result showing circulating eosinophil levels within six months before the index date.

Individuals in the study cohort will be followed from the index date until the earliest of the date of a switch in treatment, addition of either an ICS for the Tio+Olo group or of LAMA to the LABA/ICS group, discontinuation of COPD treatment, the end of the study period, or the end of continuous health plan eligibility. Main analyses will be further limited to the first year after cohort entry, with sensitivity analyses considering all available data.

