#### **8.4.2 Outcome(s)**

#### 8.4.2.1 Primary outcome(s)

The primary outcome event for effectiveness is time to first COPD exacerbation after cohort entry. The event is defined as follows:

• Severe exacerbation:

Proprietary confidential information © 2020 Boehringer Ingelheim International GmbH or one or more of its affiliated companies

- o Hospitalization with a principal discharge diagnosis of COPD.
- Moderate exacerbation:
  - o An ED visit with a discharge diagnosis of COPD, and/or
  - An antibiotic for a respiratory condition dispensed the same day as an oral corticosteroid

Time to the first COPD exacerbation will be measured from cohort entry until the occurrence of a hospitalization for COPD (severe exacerbation) or ED visit for COPD or prescription of an antibiotic and an oral corticosteroid on the same day (moderate exacerbation). Severe and moderate exacerbations will be considered as a composite for main analyses. Sensitivity analyses will stratify by exacerbation severity.

Although there is precedent for defining moderate exacerbation based on use of antibiotics for a respiratory infection without requiring concomitant oral corticosteroids, we have chosen a more restrictive definition of exacerbation. Because diagnoses listed on outpatient claims often correspond to a patient's past medical history in addition to acute problems, we expect limited ability to capture the indication for which antibiotics are prescribed. As such, including antibiotics alone as a case definition for exacerbation would introduce potentially substantial misclassification of outcome where antibiotics were truly given for non-respiratory infections. Given that our analyses will yield estimates on a ratio measure, non-differentially reduced sensitivity is a less important threat to validity than reduction of outcome specificity, which produces an expectation of bias towards the null hypothesis. In order to test our assumptions that the sensitivity of our outcome definition is not differential between the Tio+Olo and LABA/ICS groups, we would produce counts of patients with antibiotics alone during follow-up, and determine whether the proportion of potential exacerbations that we excluded through this design decision is comparable across groups.

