**BI Study Number 1237-0093** 

- o Methylxanthines
- o Muscarinic antagonists
- Short-acting muscarinic antagonists
- Use of antibiotics commonly prescribed for a respiratory condition (e.g., azithromycin)

Chronic comorbidities will be defined using diagnoses identified during all available data prior to the index date, and will include:

- Cardiovascular disease
- Charlson comorbidity index
- Diabetes
- Thyroid disease
- Renal failure
- Autoimmune disease
- Pneumonia
- Obesity\*
- Alcohol use disorder\*
- Tobacco use or cessation counselling\*
- Cancer (excluding basal cell carcinoma)

\*We anticipate limited capture of lifestyle variables known to be risk factors and potential confounders, including obesity, smoking status and excessive alcohol consumption. Although we will describe them as identified in the HIRD, bias analyses to examine the extent to which residual confounding may impact results are also planned.

Additionally to the covariates defined above, we will use the high-dimensional approach to identify variables entering a time-conditional propensity score.

Sub-populations with high or low risk of exacerbations will be defined as based on circulating eosinophils (cut-off of B-Eos 300 cells/uL) as identified based on the laboratory result value that is closest but prior to the index date (within 6 months). Additional stratification will include previous history of exacerbations in the year preceding cohort entry (with exacerbation history defined as either 1+ hospitalization or 2+ exacerbations in emergency department or outpatients settings), and among those without a history of exacerbation at baseline, based on circulating eosinophil results as noted above. We will not present results stratified by circulating eosinophil levels among those with baseline exacerbations due to low counts observed when assessing study feasibility (see Section 8.7).

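### Section 8.4.4 defines the moderate baseline exacerbation covariate by inhaled corticosteroid/antibiotic dispensings, but Section 8.4.2.1 requires an oral corticosteroid and a respiratory antibiotic on the same day; Section 7 also states a different history cut-off from 8.9.1

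*Combined protocol and SAP*

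**What the plan says.** **Outcome (8.4.2.1).** A severe exacerbation is "Hospitalization with a principal discharge diagnosis of COPD". A moderate one is "An ED visit with a discharge diagnosis of COPD, and/or" the drug criterion: "An antibiotic for a respiratory condition dispensed the same day as an oral corticosteroid". The section explains why an antibiotic without an oral steroid is not accepted: "including antibiotics alone as a case definition for exacerbation would introduce potentially substantial misclassification of outcome".

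**Baseline covariate (8.4.4).** Under a parent item for previous acute COPD exacerbation, counted as 0, 1 or 2+ over the baseline year and in the last 30 days, the moderate line reads "ED visits or dispensings of inhaled corticosteroids/antibiotics (Moderate" and the severe line "Hospitalizations (Severe". The same section lists ICS monotherapy and LAMA/ICS among prior treatments and, as a separate covariate, "Use of antibiotics commonly prescribed for a respiratory condition (e.g., azithromycin". It lists no oral corticosteroid covariate.

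**Eligibility (8.3).** To restrict the cohort to new users, the plan will "exclude any individual with use of either Tio+Olo, LABA/ICS, or LABA/LAMA/ICS" combination therapy in the year before index. ICS monotherapy is not excluded.

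**Use of the covariate.** Sections 8.4.4 and 8.9.1 build the propensity score from the pre-specified covariates plus data-derived ones.

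**History subgroups.** Section 7 divides patients at none or one versus two or more exacerbations. The abstract, the last paragraph of 8.4.4, the 8.7 table and 8.9.1 define high history as at least one hospitalisation or at least two ED/outpatient events.

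**The concern.** Prior exacerbation is the baseline counterpart of the primary outcome, so it is among the confounders that the propensity score most needs to measure correctly. The 8.4.4 wording changes the steroid route from oral to inhaled and drops the same-day pairing. In this cohort inhaled steroid is maintenance treatment, and patients on ICS alone are eligible. A covariate programmed from 8.4.4 as written would therefore mix maintenance therapy and general antibiotic use with acute events, and would miss the oral-steroid signal by which 8.4.2.1 identifies an exacerbation treated outside hospital.

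The balance check in 8.9.1 would not reveal this. Standardised differences are computed on the covariate as programmed, so good balance could be reached on the wrong quantity.

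The cut-off in Section 7 is a separate and smaller matter. The objectives section states one subgroup rule and the analysis section another.

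**Working it through.** **1. The two event definitions side by side**

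| Element | 8.4.4, baseline covariate | 8.4.2.1, outcome |
|---|---|---|
| Steroid | inhaled | oral |
| Antibiotic | unspecified | for a respiratory condition |
| Link between the two drugs | a slash, no timing | both, on the same day |
| ED visit | COPD implied by the parent item | COPD discharge diagnosis |
| Hospitalisation | COPD implied by the parent item, diagnosis position not stated | principal COPD discharge diagnosis |

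The first three rows are the substantive mismatch. In the last two, only the exact diagnosis rule is left unstated.

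**2. What each reading of the moderate line would count**

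- *Either drug alone.* Every ICS fill or antibiotic fill is an event. If each dispensing counts once, two ICS refills in the baseline year put a patient in the 2+ category without any acute event.
- *The pair, with no timing rule.* An ICS fill and an antibiotic fill are both needed. Antibiotics alone no longer count, but the steroid is still the maintenance drug.
- *A slip for oral.* The line then agrees with 8.4.2.1 apart from the same-day rule and the respiratory qualifier.

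Under the first two readings the covariate does not capture the oral-steroid event, and no other listed covariate does so. Data-derived variables might recover it, but that is not assured. The documents do not give prior ICS, antibiotic or oral-steroid use by treatment group, so neither the direction nor the size of any residual confounding can be calculated.

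**3. The two history rules**

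Section 7, counting all events equally: high if inpatient + outpatient ≥ 2. Section 8.9.1: high if inpatient ≥ 1 or outpatient ≥ 2.

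| Inpatient | ED/outpatient | Section 7 | 8.9.1 |
|---|---|---|---|
| 0 | 0 | low | low |
| 0 | 1 | low | low |
| 0 | 2+ | high | high |
| 1 | 0 | **low** | **high** |
| 1 | 1+ | high | high |
| 2+ | any | high | high |

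The rules disagree for one pattern only: exactly one hospitalisation and no other event. Following Section 7 would move those patients from high to low history.

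**4. Which rule the 8.7 counts use**

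The row labels in 8.7 carry the 8.9.1 rule. The strata add up to the stated cohorts:

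- Tio+Olo: low 1,381 + 481 + 2,739 = 4,601; high 226 + 105 + 537 = 868; total 5,469.
- LABA/ICS: low 12,351 + 4,437 + 28,733 = 45,521; high 1,820 + 670 + 5,421 = 7,911; total 53,432.

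The sums show only that each patient falls in one stratum. They do not show which event definition was used to count exacerbations.

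The share of the high-history group with the discordant pattern is not given. Under assumed shares of 10%, 25% and 50%, the number moved would be 87, 217 or 434 of 868 for Tio+Olo, and 791, 1,978 or 3,956 of 7,911 for LABA/ICS. These figures illustrate the dependence on an unknown share and are not estimates.

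**The case against.** The other side has a good case on several points.

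- *The covariate lines are shorthand.* They sit under a parent item that names acute COPD exacerbation, and the moderate and severe labels are the terms that 8.4.2.1 defines. A reader might infer that the ED and hospitalisation lines admit non-COPD events. The parent item does not support that, and for those lines a cross-reference is only a clarification. Shorthand does not explain a changed steroid route.
- *The word is a slip.* Probably. Annex 3.2 lists prednisolone codes with the outcome definitions, which fits an oral-steroid event, and Annex 3.3 lists no inhaled-steroid exacerbation code. But both annexes say that complete code lists are still to come, so they do not settle how the covariate will be built.
- *The argument against antibiotics alone concerns the outcome.* This stands. The reasoning in 8.4.2.1 is about outcome specificity, and nothing requires a covariate to copy the outcome definition. A broader baseline marker would not in itself be a contradiction. The difficulty is that the item is labelled as exacerbation but, read literally, counts maintenance treatment.
- *Other covariates limit the harm.* Separate ICS and antibiotic covariates and the data-derived variables may compensate in part. No effect on the results is shown.
- *Section 7 merely abbreviates.* Likely. The abstract cites the same source for the fuller rule, and four places agree against one.

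The text between 8.4.2.2 and 8.4.4 was not available for this review, and Annex 3.3 refers to a Section 8.4.3. A further definition there cannot be excluded, but it would leave the wording of 8.4.4 to be reconciled.

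**Conclusion.** Wrong as written, and minor. The moderate line in 8.4.4 is an operative definition for a pre-specified propensity-score covariate, and it conflicts with 8.4.2.1 on steroid route and same-day pairing. Confidence in the textual mismatch is high. Its effect on the hazard ratio is unknown and depends on whether the line is programmed literally.

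The Section 7 cut-off conflict is real but narrow. The 8.9.1 rule is fairly clearly the intended one, and only patients with one hospitalisation and nothing else are affected.

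Two stronger conclusions are tempting and not supported. A reader might infer that the history strata and the interaction analysis are also built on inhaled-steroid or antibiotic fills. The available text does not say which events define them, so that link is not shown. A reader might also take the whole high-history group in 8.7 as the number who would change stratum. That would require every such patient to have exactly one hospitalisation and no other event. It is a limit with no bearing on the likely size and does not support a higher grading. The 8.7 counts are also preliminary, with no rows for the asthma, lung cancer, interstitial lung disease or transplant exclusions.

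**What to change.** 1. In 8.4.4, replace the moderate line with the 8.4.2.1 definition: an ED visit with a COPD discharge diagnosis, and/or a respiratory antibiotic dispensed on the same day as an oral corticosteroid. Cross-refer the severe line to 8.4.2.1. Keep the 0, 1, 2+ categories and the 30-day measure.
2. In Section 7, replace the cut-off with the 8.9.1 rule.
3. In 8.4.4 and 8.9.1, state that this same event definition also serves the history strata and the interaction term.
4. In 8.7, note which event definition produced the feasibility counts.

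The cost is a few sentences in Sections 7, 8.4.4, 8.7 and 8.9.1 and one shared event definition in the program. No new data are needed.

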**BI Study Number 1237-0093** 

- o Methylxanthines
- o Muscarinic antagonists
- Short-acting muscarinic antagonists
- Use of antibiotics commonly prescribed for a respiratory condition (e.g., azithromycin)

Chronic comorbidities will be defined using diagnoses identified during all available data prior to the index date, and will include:

- Cardiovascular disease
- Charlson comorbidity index
- Diabetes
- Thyroid disease
- Renal failure
- Autoimmune disease
- Pneumonia
- Obesity\*
- Alcohol use disorder\*
- Tobacco use or cessation counselling\*
- Cancer (excluding basal cell carcinoma)

\*We anticipate limited capture of lifestyle variables known to be risk factors and potential confounders, including obesity, smoking status and excessive alcohol consumption. Although we will describe them as identified in the HIRD, bias analyses to examine the extent to which residual confounding may impact results are also planned.

Additionally to the covariates defined above, we will use the high-dimensional approach to identify variables entering a time-conditional propensity score.

Sub-populations with high or low risk of exacerbations will be defined as based on circulating eosinophils (cut-off of B-Eos 300 cells/uL) as identified based on the laboratory result value that is closest but prior to the index date (within 6 months). Additional stratification will include previous history of exacerbations in the year preceding cohort entry (with exacerbation history defined as either 1+ hospitalization or 2+ exacerbations in emergency department or outpatients settings), and among those without a history of exacerbation at baseline, based on circulating eosinophil results as noted above. We will not present results stratified by circulating eosinophil levels among those with baseline exacerbations due to low counts observed when assessing study feasibility (see Section 8.7).

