#### *Inclusion Criteria:*

- 1. At least one prescription for Tio+Olo combined inhaler or a LABA/ICS combined inhaler between 1 January 2013 and 31 March 2019.
  - a) The first dispensing of either Tio+Olo or LABA/ICS combined inhaler will be defined as the index date.
  - b) For the main analyses, only fixed dose combination (FDC) inhalers will be included. Sensitivity analyses will also accept free combinations of LABA/ICS.
- 2. At least one diagnosis of COPD at any time prior to the index date.
- 3. At least one year of continuous medical and pharmacy health plan eligibility prior to the index date will be required to allow a baseline period for the covariates and identification of new use of the study drugs.

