#### 8.5 DATA SOURCES

This study will be conducted using the HIRD, a large administrative healthcare database maintained by HealthCore for use in health outcomes and pharmacoepidemiologic research. The HIRD includes longitudinal medical and pharmacy claims data from health plan

members across the United States (US). Member enrollment, medical care (professional and facility claims), outpatient prescription drug use, outpatient laboratory test result data, and health care utilization may be tracked for health plan members in the database dating back to January 2006, and with diagnoses recorded in International Classification of Disease, Version 10 (ICD-10) since October, 2015. Laboratory result data are additionally available for those tests that have been performed using two large, national reference laboratories (Quest and LabCorp) [R14-4278]. The database has been used for the study of numerous diseases, including studies of COPD [R19-2324; R19-2321; R19-2323; R19-2322; P15-11025; P14-12233].

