#### 8.7 STUDY SIZE

Preliminary counts of FDC Tio+Olo and ICS/LABA users in the HIRD are shown here:

	Tio+Olo		ICS/LABA	
	N	%	N	%
New users	8,233	100.0	341,352	100.0
At least 12 months of pre-index eligibility	6,263	76.1	187,093	54.8
Age 40+	6,126	97.8	136,310	72.9
At least 1 diagnosis of COPD	5,469	89.3	53,432	39.2
At least 1 eosinophil % result prior to the index date	2,207	40.4	19,407	36.3
Eosinophil result (N, % of those with				
a result)				
0-2%	1,059	48.0	8,907	45.9
2-4%	745	33.8	6,698	34.5

D 1	' C	Y 11 1 Y 1	0 177	01. 011. 1
Proprietary confidential	information © 2020 Boehring	ger Ingelheim International	GmbH or one or more of	of its affiliated companies

4%+	403	18.3	3,802	19.6
Eosinophil result, patients with low				
exacerbation history(0 inpatient and				
0-1 outpatient events at baseline, N,				
%)				
<300 cells/uL	1,381	30.0	12,351	27.1
≥300 cells/uL	481	10.5	4,437	9.7
Unknown	2,739	59.5	28,733	63.1
Eosinophil result, patients with high				
exacerbation history (1+ inpatient or				
2+ outpatient events at baseline, N,				
%)				
<300 cells/uL	226	26.0	1,820	23.0
≥300 cells/uL	105	12.1	670	8.5
Unknown	537	61.9	5,421	68.5

In a recent analysis of the risk of exacerbations based on Clinical Practice Research Datalink (CPRD), a total of 2,000 patients per cohort detected a 15% difference in risk of a first exacerbation (hazard ratio 0.85) with over 90% power. As such, overall analyses are expected to have adequate power. Analyses that are stratified based on the presence of claims-based indicators of exacerbation and/or limited to individuals with specific eosinophils levels will be more limited. Given low expected sample size, stratification by eosinophil results within individuals with exacerbations at baseline will not be performed.

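### Comorbidities are captured over a look-back of unequal length that is not a named propensity score covariate, and pneumonia history has no recency window

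*Combined protocol and SAP*

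**What the plan says.** Section 8.4.4 uses two measurement windows. For prior COPD treatments, exacerbations and other respiratory drugs, "Additional characteristics will be defined during the 12-month pre-index baseline period"; exacerbations are also counted in the 30 days before entry. For comorbidities, "Chronic comorbidities will be defined using diagnoses identified during all available data prior to the index date". The second list has eleven items: cardiovascular disease, Charlson index, diabetes, thyroid disease, renal failure, autoimmune disease, pneumonia, obesity, alcohol use disorder, tobacco use and cancer.

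The floor on look-back is in the inclusion criteria (section 8.3): "At least one year of continuous medical and pharmacy health plan eligibility prior to the index date will be required". The ceiling follows from section 8.5, where records "may be tracked for health plan members in the database dating back to January 2006", and from the index window, "between 1 January 2013 and 31 March 2019".

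The demographic covariates include "Calendar year of cohort entry", age and insurance type. Enrolment or look-back length is not listed. Sections 8.4.4 and 8.9.1 add data-derived high-dimensional variables without naming them or their windows, and section 8.4.4 calls the score time-conditional without defining the term. Section 8.9.1 judges balance by standardized differences in patient characteristics, with 0.10 as the limit. Sections 8.6 and 8.11 discuss misclassification of outcome and exposure and missing data, but not unequal ascertainment time for covariates.

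**The concern.** A patient observed for ten years has had more chances to acquire a diagnosis code than an equally ill patient observed for one. If one arm tends to have the longer history, equal true disease appears as unequal recorded disease. Weighting to equal recorded prevalence then over-represents truly ill patients in the arm with the shorter history. The balance table would look satisfactory, because it compares only what was recorded.

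Pneumonia raises a separate problem. It is an acute event, and hospitalization for it is the first secondary outcome (section 8.4.2.2), yet its history is one all-time variable. An episode ten years ago and one last month get the same value. Recent pneumonia could plausibly influence both whether a patient is started on an ICS and the risk of another episode, so recency is where confounding would be expected. Exacerbation history, by contrast, gets 12-month and 30-day windows.

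**Working it through.** **Range of look-back.** 1 January 2006 to 1 January 2013 is 7.0 years; to 31 March 2019 it is 13.2 years. The minimum is 1 year. The growth of the ceiling depends only on index date, which the calendar-year covariate already addresses. What remains is variation within an index year: two patients of the same age, insurance type and 2017 index date could have 1 and 10 years of history.

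**The plan's own evidence by arm (section 8.7).** The row "At least 12 months of pre-index eligibility" reproduces: 6,263/8,233 = 76.1% for Tio+Olo and 187,093/341,352 = 54.8% for LABA/ICS, a gap of 21.3 points. After the age and COPD steps, 5,469/6,263 = 87.3% of those Tio+Olo users remain, but only 53,432/187,093 = 28.6% of the LABA/ICS users. About 71% of the LABA/ICS patients behind the 54.8% are therefore not in the cohort.

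**Illustration of the mechanism.** The documents give no look-back distribution, true prevalence, coding rate or comorbidity-outcome rate ratio; all are assumed here.

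1. If prior enrolment is exponential with mean m months, the share reaching 12 months is q = exp(−12/m), so m = −12/ln(q). With q = 0.761 and 0.548, m = 43.9 and 20.0. Mean look-back among those kept is m + 12 = 55.9 v 32.0 months.
2. With coding rate r per year, the chance that a true condition is recorded is S = 1 − exp(−r)/(1 + r·m/12).
3. Take true prevalence p = 0.30 in both arms and no false positives. The weights set recorded prevalence in LABA/ICS to p·S_T. True prevalence there becomes p′ = p·S_T + (1 − p·S_T) × p(1 − S_L)/(1 − p·S_L), where T is Tio+Olo and L is LABA/ICS.
4. The spurious factor on the hazard ratio is (1 + p(RR − 1))/(1 + p′(RR − 1)).

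For r = 0.2: S_T = 0.53 and S_L = 0.39, so recorded prevalence is 15.8% v 11.6%. Then p′ = 0.158 + 0.842 × 0.208 = 0.334. The factor is 1.15/1.167 = 0.986 at RR 1.5 and 1.30/1.334 = 0.975 at RR 2.0.

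| Codes per year | S_T | S_L | Recorded SMD before weighting | True prevalence in LABA/ICS after weighting | Factor, RR 1.5 | Factor, RR 2.0 |
|---|---|---|---|---|---|---|
| 0.2 | 0.53 | 0.39 | 0.12 | 33.4% | 0.986 | 0.975 |
| 0.4 | 0.73 | 0.60 | 0.10 | 33.3% | 0.986 | 0.975 |
| 1 | 0.92 | 0.86 | 0.04 | 31.7% | 0.993 | 0.987 |
| 2 | 0.98 | 0.97 | 0.01 | 30.4% | 0.998 | 0.997 |
| 4 | 0.999 | 0.998 | 0.001 | 30.0% | 0.9998 | 0.9997 |

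Holding LABA/ICS at 32 months and coding at 0.2 to 0.4 per year, a look-back gap of 12 months gives factors of 0.985 to 0.992, and a gap of 6 months 0.992 to 0.996.

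A second calculation gave every patient in an arm that arm's mean look-back, with sensitivity 1 − exp(−rate × years), prevalence 20% or 40%, rates of 0.15 to 1.2 per year and RR 2. For 4.5 v 2.7 years the factors are 0.97 to 0.99 and the induced standardized difference in true disease is 0.02 to 0.09. For 3.5 v 3.0 years the factors are 0.99 to 1.00. If LABA/ICS had the longer history, the direction would reverse.

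**Fixed 12-month window.** In the second calculation it removes the artefact when true prevalence is equal, but its sensitivity is only 14% to 70%, against 31% to 94% with all data. When true prevalence differs (25% v 20%, either way round), it leaves an absolute standardized difference of 0.04 to 0.11, and all available data leave 0.005 to 0.14. Neither choice dominates.

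**The case against.** Using all available history is a defensible choice for chronic disease because it finds more of it. Calendar year removes the growth in the ceiling, age and insurance type partly track enrolment, and data-derived variables may pick up more, including recent pneumonia. Respiratory antibiotic use in the baseline year is a rough proxy for the latter. Section 8.4.1 points to a section 8.9.2 that is not in the available text, so a look-back sensitivity analysis cannot be called absent. These points stand. They narrow the concern but do not close it: none measures individual enrolment length, none guarantees a recent-pneumonia term, and a sensitivity analysis would not put look-back into the main score.

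A reader might infer from section 8.7 that Tio+Olo patients have the longer history and that the primary hazard ratio is therefore biased in their favour. The documents do not support that. The eligibility row precedes restrictions that remove about 71% of those LABA/ICS users, and requiring a COPD diagnosis at any earlier time may itself select longer histories. The 56 v 32 month figures extrapolate one point through an assumed distribution.

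A reader might also infer that all eleven comorbidities err in the same direction and add up. That is not shown. It would require each item to raise outcome risk; Charlson is a composite index; and diabetes, renal failure and the broad cardiovascular group may be coded often enough for the effect to vanish. No joint calculation is available.

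**Conclusion.** The point holds in a limited form. Ascertainment time varies between patients, its length is not a named covariate, and the balance check cannot reveal any resulting imbalance in true disease. Whether the arms differ in look-back after all restrictions, and in which direction, is unknown. If they do, the shift is roughly 0% to 3% in the hazard ratio per under-recorded risk factor and near zero for conditions coded several times a year. That is small beside the hazard ratio of 0.85 discussed in section 8.7. These sizes depend on assumed look-back, prevalence, coding rates and rate ratios.

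The missing recency window for pneumonia needs none of those assumptions: it follows from comparing how section 8.4.4 treats pneumonia with how it treats exacerbations. The size of any bias from it cannot be computed from the documents. Both gaps are worth closing because it costs little, not because material bias has been demonstrated.

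**What to change.** 1. Add months of continuous pre-index eligibility, as a continuous variable, to the named propensity score covariates, and report it by arm in the balance table before and after weighting. If earlier, interrupted spells of enrolment also count as available data, use total months observed. In the illustration this removes the artefact when true prevalence is equal and disease does not depend on look-back.
2. Add pneumonia in the 12 months and in the 30 days before index as named covariates, and keep the all-history variable.
3. As a sensitivity analysis only, repeat the primary and pneumonia analyses with comorbidities measured in a fixed 12-month window.

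The cost is three covariates from data already held and one extra run. The fixed window misses more chronic disease, so a difference from the main result should be read with that in mind.
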